## **12. STATISTICAL CONSIDERATIONS**

### **12.1 Study Design/Endpoints**

This is a pilot study examining the feasibility of using acquisition of a resistance mutation as the primary endpoint for a clinical trial. NSCLC patients with EGFR mutations are highly likely to respond well to EGFR TK inhibition with either first-generation EGFR TKIs (erlotinib, gefitinib) or with the second-generation irreversible inhibitor BIBW 2992, but resistance ultimately develops, see Background. Current literature consistently estimates that fifty percent of resistance to first-generation TKIs is due to the development of a secondary EGFR mutation in exon 20, the point mutation T790M. Since the novel irreversible pan-HER inhibitor BIBW 2992 is highly active in lung cancers harboring activating EGFR mutations and can inhibit the EGFR T790M moiety in pre-clinical studies, a key question is whether BIBW 2992 can suppress the development of clinical resistance via T790M in lung cancer patients.

The study will consist of 24 TKI-naïve patients with mutations in EGFR. Given our relatively large population of referral patients at DF/HCC with EGFR mutations and the collaboration with a few select other centers, This sample size was felt to be feasible to enroll within a three year time period. Each subject will be expected to remain on therapy for approximately 10 months. Therefore within 3.5 years it is expected that we will complete at least 16 of the progression biopsies.

All patients will initially be treated with BIBW 2992 at 40 mg daily, though as in other studies with this compound, dose escalation to 50 mg will be permitted for individual patients after one cycle if there are minimal adverse events at 40 mg. Tumor tissue biopsy for comprehensive genomic profiling is mandatory at the time of acquired resistance (clinical progression). The primary endpoint will be to determine the proportion of patients with T790M resistance mutations at the time of progression. The data collected will be vital in determining the optimal strategy for future studies comparing the efficacy of BIBW 2992 to first-generation EGFR TKIs.

The primary objective is:

1. To determine the proportion of patients that have a T790M mutation on their progression biopsy and to compare this with published data for first-generation EGFR tyrosine kinase inhibitors

The secondary objectives are:

1. To estimate the response rate
2. To estimate the progression-free and overall survival
3. To describe the safety of obtaining repeat tumor biopsies for genotype analysis
4. To describe other mechanisms of resistance (besides T790M) observed on the progression biopsies

5. To explore the results of experimental CTC-derived genotype assessed from serial blood samples taken during therapy with BIBW 2992 and to compare CTC-derived results with those from the progression biopsies

## 12.2 Sample Size/Power Calculation for the Primary Endpoint

Based on prior data the rate of T790M at the time of progression on first-generation EGFR TKIs (gefitinib/erlotinib) is 50%.

The null hypothesis is that BIBW 2992 therapy yields the same rate of T790M at the time of progression (50%).

It is expected that approximately 6 of the patients will not undergo a repeat biopsy, despite consenting to the biopsy at the time of enrollment. Reasons for not having a biopsy may include patient withdrawal of consent or not having a lesion that is safe and feasible to biopsy at the time of progression. Therefore, power calculations were performed assuming there would be 18 biopsies performed.

With 18 biopsies and a significance level of 0.05, and using a one-sided binomial test, we can achieve 86% power to detect the alternative hypothesis that BIBW 2992 therapy yields a 20% rate of T790M at the time of progression. The alternate hypothesis implies that BIBW 2992 may be better at suppressing T790M as a mechanism of acquired drug resistance.

## 12.3 Data to Be Analyzed

Evaluable for the primary endpoint (acquisition of T790M): All patients who undergo a repeat biopsy will be evaluable for acquisition of T790M. If the results of this test are not interpretable due to technical failure of the assay, T790M will be assumed to be present (the more conservative assumption in terms of affecting the primary endpoint). Patients that do not undergo a repeat biopsy will not be included in the primary endpoint analysis.

Evaluable for toxicity. All participants who receive at least one dose of study treatment will be evaluable for toxicity from the time of their first treatment.

Evaluable for objective response. Only those participants who have measurable disease present at baseline, have received at least one cycle of therapy, and have had their disease re-evaluated will be considered evaluable for response. These participants will have their response classified according to the definitions stated below. (Note: Participants who exhibit objective disease progression or die prior to the end of cycle 1 will also be considered evaluable.)

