### 1.2 Primary Objective

1. To determine the proportion of patients that have a T790M mutation on their progression biopsy and to compare this with published data for first-generation EGFR tyrosine kinase inhibitors

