## 7. MOLECULAR AND CORRELATIVE STUDIES

### 7.1 Repeat Biopsies for Molecular Testing

It is expected that all patients will undergo a repeat tumor tissue biopsy at the time of removal from study treatment. Ideally, the lesion to be biopsied should be new or growing on BIBW 2992 therapy. The purpose of this biopsy is to assess for the presence or absence of the resistance mutation T790M. This is the primary end-point of the study. In most cases, the repeat biopsy will be at the time of clinical progression. If a patient is being removed from treatment for reasons other than clinical progression (e.g. withdrawal of consent, intolerance of side effects, etc) then a repeat biopsy is desirable but not required.

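### Section 12.3 admits every repeat biopsy to the primary analysis, including optional ones taken off progression, while the endpoint and the 50% null concern biopsies at progression

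*Combined protocol and SAP*

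**What the plan says.** The primary objective (Section 1.2) is: "To determine the proportion of patients that have a T790M mutation on their progression biopsy". Section 12.1 repeats the time point: "The primary endpoint will be to determine the proportion of patients with T790M resistance mutations at the time of progression". Section 5.1 ties the endpoint to a repeat biopsy taken at clinical progression. In Section 12.2 the null (50%) and the alternative (20%) are both rates at progression. The 50% comes from 24 of 48 tumours with acquired resistance to gefitinib or erlotinib (Section 2.2.2).

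Section 12.3 then defines the primary set: "All patients who undergo a repeat biopsy will be evaluable for acquisition of T790M". It excludes only patients who have no repeat biopsy, and it counts technically failed assays as T790M present. It has no progression condition.

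Section 7.1 uses *repeat biopsy* more widely. "It is expected that all patients will undergo a repeat tumor tissue biopsy at the time of removal from study treatment", it says, and "In most cases, the repeat biopsy will be at the time of clinical progression". It goes on: "If a patient is being removed from treatment for reasons other than clinical progression", giving withdrawal of consent and intolerance as examples, "then a repeat biopsy is desirable but not required".

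**The concern.** The set that 12.3 describes is wider than the population to which the endpoint and the null refer. A patient who stops for intolerance and agrees to the optional biopsy has had a repeat biopsy, so 12.3 counts that patient. The tumour may not have become resistant, in which case absence of T790M says nothing about whether BIBW 2992 suppressed this route of resistance.

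The likely direction is an inference. Sections 2.3.2 and 2.4 describe T790M before treatment as low-level and missed by standard sequencing, and 2.3.2 describes the resistant clone growing under a TKI that cannot inhibit it. A rate below 50% off progression is therefore plausible, but it is not stated anywhere.

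This is the trial's only hypothesis test, on about 18 observations, so one or two samples matter. An analyst who follows 12.3 and one who follows the endpoint wording could use different denominators, and the plan does not say which governs.

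**Working it through.** **Inputs from Section 12.2.** 24 enrolled (12.1) less about 6 without a biopsy = 18; null rate 0.50; alternative 0.20; one-sided binomial test at 0.05; stated power 86%.

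**Inputs assumed, because the documents give none.** m = number of off-progression biopsies in the set; q = their T790M rate; f = number of technical failures counted as present.

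**1. The plan's own figure.** The cut-off c is the largest integer with P(X ≤ c | n, 0.5) ≤ 0.05. For n = 18:
- P(X ≤ 5) = 12,616/262,144 = 0.0481, and P(X ≤ 6) = 0.1189, so c = 5.
- Power = P(X ≤ 5 | 18, 0.20) = 0.867, which agrees with the stated 86%.

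**2. Type I error with off-progression samples among the 18.** Let the true rate at progression be 0.50. The count of T790M-present results is X = f + Bin(n − m − f, 0.5) + Bin(m, q). With f = 0:
- m = 1: (1 − q)·P(Bin(17, 0.5) ≤ 5) + q·P(Bin(17, 0.5) ≤ 4) = (1 − q)·0.0717 + q·0.0245.
- m = 2: (1 − q)²·0.1051 + 2q(1 − q)·0.0384 + q²·0.0106, the three probabilities being Bin(16, 0.5) at or below 5, 4 and 3.

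| q | m = 1 | m = 2 |
|---|---|---|
| 0 | 0.072 | 0.105 |
| 0.10 | 0.067 | 0.092 |
| 0.25 | 0.060 | 0.074 |
| 0.50 | 0.048 | 0.048 |

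At q = 0 the expected observed proportion falls from 50% to 17 × 0.5/18 = 47.2% (m = 1) or 16 × 0.5/18 = 44.4% (m = 2).

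**3. Dependence on n.** One T790M-absent sample in the total (m = 1, q = 0, f = 0):

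| Total n | c | Attained level, m = 0 | Type I error, m = 1 |
|---|---|---|---|
| 16 | 4 | 0.038 | 0.059 |
| 17 | 4 | 0.025 | 0.038 |
| 18 | 5 | 0.048 | 0.072 |
| 19 | 5 | 0.032 | 0.048 |

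If one or two absent samples come on top of 18 progression biopsies (n = 19 or 20, c = 5), the error is P(Bin(18, 0.5) ≤ 5) = 0.048 in both cases.

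**4. Effect of the technical-failure rule.** For n = 18 and q = 0, one failure gives 0.025 (m = 0), 0.038 (m = 1) and 0.059 (m = 2). Two failures with m = 2 give 0.029.

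**5. Effect on a single result.** Adding one absent sample moves 5 of 17 (p = 0.072) to 5 of 18 (p = 0.048), which crosses 0.05. It moves 5 of 16 (p = 0.105) only to 5 of 17 (p = 0.072), which does not.

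**The case against.** The strongest reply is that the documents already settle the matter. Section 5.1 puts endpoint, repeat biopsy and clinical progression in one sentence, and 12.3 defines who is evaluable for that endpoint. Section 12.2 explains missing biopsies partly by the lack of a lesion safe to biopsy at progression. It also lists withdrawal of consent, one of 7.1's two examples of stopping off progression, so part of that group is expected to have no biopsy. The repeat-biopsy note in Section 9 refers to the time of progression, as do 12.9 and Appendix 3, Section 8.1. Section 12.4 requires a summary of who was included in the analyses, so the set used would be disclosed.

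This shows that progression biopsies were probably intended. It does not remove the defect. Section 12.3 states a rule for the analysis set, none of the other sections overrides it, and 12.9 carries a progression qualifier that 12.3 lacks. Disclosure under 12.4 would reveal the choice without fixing it in advance.

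The reply is right about size. The planned n = 18 is unfavourable because its attained level is already close to 0.05. The higher figures require samples that all lack T790M and no technical failures.

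**Conclusion.** The point holds as a mismatch between the analysis set in 12.3 and the endpoint it serves, and should be fixed. At 18 biopsies in total, one or two off-progression samples with a T790M rate of 0 to 25% would put the one-sided error between 0.060 and 0.105, if the true rate at progression is 50% and no assay fails. The number of such samples, their rate and the number of failures are all assumptions.

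Three stronger readings are tempting and unsupported:
- A reader might infer that the error rate is in fact inflated. The documents do not show that any off-progression biopsy will be taken or that T790M is rarer in them. At a 50% rate nothing changes, and at n = 17 or 19 one absent sample leaves the error below 0.05.
- A reader might infer that one such sample decides the trial. It can, but step 5 shows that it need not.
- A reader might take the defect to include the meaning of progression: RECIST in 5.10, clinical in 7.1 and 12.1, and where symptomatic deterioration (note to Table 3) belongs. Those are secondary clarifications. The mismatch exists under either meaning.

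**What to change.** In 12.3, add the qualifier that 5.1, 12.1 and 12.9 already carry, so that the primary set is patients with a repeat biopsy taken at the time of progression. Keep the technical-failure rule. Report off-progression biopsies separately, and add a sensitivity analysis of all biopsies.

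State explicitly whether a biopsy at progression counts when BIBW 2992 had been stopped earlier for another reason. The calendar in Section 9 marks the repeat biopsy in the survival follow-up column as well as at the off-study visit, and patients who stop without objective progression continue tumour assessments where possible. A qualifier limited to progression on treatment would drop such biopsies without saying so.

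The cost is a wording change. Discontinuation data (12.4), later tumour assessments and subsequent therapies (Section 9) are already planned. With 18 progression biopsies the design is unchanged. If samples leave the set, power at a 20% rate falls from 0.867 (n = 18, c = 5) to 0.758 (n = 17, c = 4) or 0.798 (n = 16, c = 4). The uneven drop comes from the discreteness of the exact test.

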## **3. PARTICIPANT SELECTION**

### **3.1 Eligibility Criteria**

Participants must meet the following criteria on screening examination to be eligible to participate in the study:

- 3.1.1 Participants must have histologically or cytologically confirmed stage IIIB, IV, or recurrent non-small cell lung cancer
- 3.1.2 A somatic mutation in epidermal growth factor receptor (EGFR) must be present as documented by a CLIA-certified laboratory.
- 3.1.3 There must be radiographic measurable or evaluable disease
- 3.1.4 Participants must be willing, at the time of signing consent, to agree to a future biopsy of their tumor tissue at the time of disease progression, provided such a biopsy is safe and

CONFIDENTIAL

This document is confidential. Do not disclose or use except as authorized.

feasible at that time. This biopsy will be subjected to genetic analyses to attempt to identify the mechanism of acquired drug resistance.

- 3.1.5 Performance status must be 0, 1 or 2 on the Eastern Cooperative Oncology Group scale
- 3.1.6 Age must be  $\geq$  18 years
- 3.1.7 Participants must have normal organ and marrow function as defined below:
  - Absolute neutrophil count  $\geq$  1,500/mcL
  - Platelets  $\geq$  100,000/mcL
  - AST (SGOT)/ALT (SGPT)  $\leq$  3 X institutional upper limit of normal (ULN) or, if liver metastases present  $\leq$  5 X ULN
  - Total bilirubin  $\leq$  1.5 X ULN
  - Creatinine  $\leq$  1.5 X ULN or creatinine clearance  $\geq$  60 mL/min/1.73 m^2 for subjects with creatinine levels  $\geq$  1.5 x ULN
- 3.1.8 The effects of BIBW 2992 on the developing human fetus are unknown. For this reason, women of child-bearing potential and men must agree to use adequate contraception (hormonal or barrier method of birth control; abstinence) prior to study entry and for the duration of study participation. Should a woman become pregnant or suspect she is pregnant while participating in this study, she should inform her treating physician immediately.
- 3.1.9 Participants must have the ability to understand and the willingness to sign a written informed consent document.

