### 7.1.3 Molecular Assessment of Repeat Biopsy Tissue

Repeat biopsy tumor tissue will be handled under the following procedures. One slide will be routed to anatomic pathology, to confirm that the lesion biopsied is malignant and appears as expected from a histologic standpoint given the presumptive diagnosis. The majority of the sample will undergo genotyping analysis with the SNaPshot platform as described in Section 2.3.1. Note: if the biopsy is taken at another hospital besides Massachusetts General Hospital, anatomic confirmation of the diagnosis should still occur at the hospital performing the biopsy (using as little material as possible). The rest of the material will be formalin-fixed and paraffin-embedded, and should be routed to [name] at MGH for analysis with the SNaPshot platform. Samples should be shipped with a requisition form (see Appendix 4) to:

The primary use of the material obtained from repeat biopsies will be to assess T790M status from resistant specimens. We will also determine if there is MET amplification, another validated mechanism of acquired resistance. However, when there is sufficient tissue, we will perform other exploratory genomic, proteomic and expression profiling and attempt to develop patient-specific tumor models *in vitro* and *in vivo*. The establishment of such models will allow us to functionally validate or refute the hypothesized mechanisms of resistance to BIBW 2992. We have had success with these techniques in the past and will perform these studies in collaboration with [name] who has an established track record of developing xenograft tumor models and cell lines from patient specimens. Leftover material will be returned to the participating institution at the completion of the study.

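### A readable but tumor-poor progression biopsy can count as T790M absent, because 12.3 does not require the patient's known EGFR mutation to be found in the same sample

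*Combined protocol and SAP*

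**What the plan says.** Section 12.3 defines the primary analysis set: "All patients who undergo a repeat biopsy will be evaluable for acquisition of T790M". It adds one protective rule: "If the results of this test are not interpretable due to technical failure of the assay, T790M will be assumed to be present", and explains that this is the cautious direction for the primary endpoint. Patients without a repeat biopsy are left out.

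Section 7.1.3 describes the handling of the specimen: "One slide will be routed to anatomic pathology, to confirm that the lesion biopsied is malignant". Most of the remainder goes to the SNaPshot panel. No minimum tumor content is set, and nothing is said about what follows for the endpoint if the slide shows no tumor.

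Every patient enters with a known marker of their tumor. Under 3.1.2, "A somatic mutation in epidermal growth factor receptor (EGFR) must be present as documented by a CLIA-certified laboratory". Section 2.3.1 lists EGFR among the genes the panel reads. Neither 7.1.3 nor 12.3 uses that marker to check a negative T790M call.

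Section 12.2 sets the test: "With 18 biopsies and a significance level of 0.05, and using a one-sided binomial test", the plan states that "we can achieve 86% power to detect the alternative hypothesis", which is that "BIBW 2992 therapy yields a 20% rate of T790M at the time of progression". The null rate is 50%.

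**The concern.** A core or aspirate made up largely of stroma, necrosis or normal lung can amplify well and read as wild-type EGFR. The assay has then worked, so the technical-failure rule does not apply, and on the natural reading of 12.3 the patient counts as T790M absent. Such a result carries little information about whether the resistant tumor has T790M.

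The trial hopes to show a low rate, so an uninformative sample counted as absent moves the result toward the hoped-for conclusion. That is the opposite of the caution 12.3 applies to failed assays. With a cut-off at a handful of patients out of 18, one or two doubtful negatives could decide the primary test. How to score them is best settled before results are known.

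**Working it through.** **Inputs.** From 12.2: n = 18, one-sided level 0.05, null rate 0.50, alternative 0.20, stated power 86%. From 2.2.2: the historical rate, 24/48 = 50%. Not in the documents: k, the number of the 18 samples that read as wild type for want of tumor DNA. I take k = 1 to 3 as an assumption and also show a wider range as a probability f.

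**Step 1: reproduce the plan's figure.** Reject when X ≤ c, with c the largest value for which P(X ≤ c | 18, 0.5) ≤ 0.05.

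- P(X ≤ 5) = (1 + 18 + 153 + 816 + 3,060 + 8,568)/2^18 = 12,616/262,144 = 0.0481.
- P(X ≤ 6) = (12,616 + 18,564)/262,144 = 0.119, which is too large, so c = 5.
- Power = P(X ≤ 5 | 18, 0.2) = 0.867, which agrees with the stated 86%.

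The exact level is already close to 0.05, so there is almost no slack.

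**Step 2: k uninformative samples counted as absent.** They cannot add a positive, so X follows Binomial(18 − k, p) while the cut-off stays at 5. The expected observed rate under the null is 0.5(18 − k)/18.

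| k | Expected observed rate | Type I error, P(X ≤ 5 \| 18 − k, 0.5) | Apparent power at 20% |
|---|---|---|---|
| 0 | 50% | 0.048 | 0.867 |
| 1 | 47% | 0.072 | 0.894 |
| 2 | 44% | 0.105 | 0.918 |
| 3 | 42% | 0.151 | 0.939 |

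If instead each sample is uninformative with probability f, the null rate becomes 0.5(1 − f). The type I error is then 0.073, 0.108, 0.209 and 0.355 for f = 0.05, 0.10, 0.20 and 0.30.

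**Step 3: the opposing rule.** Let a fraction t fail technically and be scored present. The observed null rate is q = 0.5(1 − f − t) + t. With f = 0.10:

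| t | q | Type I error |
|---|---|---|
| 0 | 0.45 | 0.108 |
| 0.05 | 0.475 | 0.073 |
| 0.10 | 0.50 | 0.048 |
| 0.20 | 0.55 | 0.018 |

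Equal rates cancel under the null. More failures than false negatives make the test conservative.

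**Step 4: what each remedy costs.** Excluding k samples means finding a new cut-off for n = 18 − k. Scoring them present keeps the cut-off at 5, so the other 18 − k samples may contain at most 5 − k positives.

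| k | Excluded: n, cut-off | Level | Power at 20% | Scored present: level | Power at 20% |
|---|---|---|---|---|---|
| 1 | 17, 4 | 0.025 | 0.758 | 0.025 | 0.758 |
| 2 | 16, 4 | 0.038 | 0.798 | 0.011 | 0.598 |
| 3 | 15, 3 | 0.018 | 0.648 | 0.004 | 0.398 |

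Power under exclusion does not fall smoothly, because the cut-off moves in whole patients.

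**The case against.** **The text does not order this scoring.** 12.3 says nothing about tumor-poor samples, and an analyst might stretch technical failure to cover them. That is fair, but the failure rule is tied to the assay and a readable result is not a failed assay. The silence is what needs closing.

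**Safeguards exist.** 7.1.3 describes one specimen being divided, so the pathology slide is evidence about the genotyped material, though not proof. Section 7.1 prefers a new or growing lesion. 7.1.1 sets an 8 mm minimum for thoracic lesions and restricts bone sites because processing damages DNA. 7.1.2 aims for at least two cores and three aspirates, and the platform in 2.3.1 is validated. All of this makes a tumor-free sample less likely. None of it is a rule on evaluability.

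**The net bias is not shown.** This stands. Technical failures scored present push the other way (Step 3). The 50% null is itself a detected rate: if the 24 of 48 carried similar false negatives, the figures in Step 2 overstate the inflation. The documents do not say whether those series used such a control.

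**The remedy is not free, and this is a pilot.** Both are true. Step 4 shows the power cost, and 2.3.1 does not list which EGFR variants are read, while 3.1.2 admits any somatic EGFR mutation. The pilot label limits the consequences, but 12.2 still sets a formal test on this endpoint.

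**Conclusion.** The gap is real. A readable wild-type result from tumor-poor tissue would count as T790M absent, and each such sample moves the test toward suppression. If 1, 2 or 3 of 18 samples are of this kind and nothing offsets them, the one-sided type I error is 0.072, 0.105 or 0.151 instead of 0.048; one is enough to pass 0.05. This rests on an assumed count, on no technical failures scored present, and on a historical 50% free of the same error.

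A reader might infer more than the documents support:

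- That the trial is biased toward showing suppression and its false-positive rate is inflated. This is conditional, since neither the rate of technical failures nor the false-negative rate in the historical series is given.
- That any biopsy without usable DNA counts as absent. A sample that cannot be amplified would normally be a technical failure, which 12.3 scores as present.
- That the pathology check says nothing about the genotyped tissue. It lowers the risk; it simply has no stated consequence.

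This is a cheap and worthwhile improvement to the definition of the primary endpoint, not proof that the design fails.

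**What to change.** In 12.3, with a matching sentence in 7.1.3:

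1. Score T790M present whenever it is detected, and keep the existing rule for technical failures.
2. Score it absent only if the patient's known EGFR mutation is detected in the same progression sample. Where the panel does not cover that mutation, require that the pathology review already planned confirms tumor in the biopsy.
3. Treat a sample with neither T790M nor the known mutation as uninformative. Exclude it from the primary analysis, as 12.3 already does for patients without a biopsy, and report a sensitivity analysis scoring it as present, in line with the existing cautious rule. Scoring it present in the primary analysis would cost more power from the second such sample on (Step 4).
4. In 12.2, state that the power rests on 18 informative biopsies.

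**Cost.** Mainly wording, plus a record of whether the panel reads each patient's mutation. No new assay is needed where it does. The price is power: 0.758, 0.798 or 0.648 with 17, 16 or 15 informative samples, unless enrollment grows. As an illustration, if 2 of 20 biopsies were uninformative (an assumption) and 6 of 24 patients have no biopsy as 12.2 expects, 18 informative biopsies need 20/0.75 = 26.7, so 27 patients rather than 24.

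**Limit.** Finding the known mutation shows that tumor DNA was read. It does not show that T790M at a low level would have been seen.

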## **2.3 Molecular Techniques Background**

### **2.3.1 SNaPshot Genotyping Platform**

Recently, MGH implemented a multiplex molecular diagnostics platform (SNaPshot). This assay utilizes formalin-fixed paraffin-embedded tissue to quickly and economically identify 58 commonly mutated loci in 13 key oncogenes: EGFR, K-RAS, N-RAS, APC, BRAF, FLT3, JAK2, Kit, Notch, PI3K, PTEN, TP53, and beta-catenin. The DNA of interest is amplified using multiplexed PCR. Genotypes are determined using a single-base extension sequencing reaction, in which allele-specific probes interrogate loci of interest and are extended by fluorescently labeled dideoxynucleotides. The allele-specific probes have different sizes and are subsequently resolved by electrophoresis and analyzed by an automated DNA sequencer. Amplifications of EGFR, HER2, and MET and translocations in ALK are assessed using multicolor FISH assays. The SNaPshot profile has been validated and is performed in a CLIA-certified lab. It is used in place of routine EGFR and K-RAS mutation testing at our center, as it provides additional information that may be used to identify specific genetic abnormalities that correlate with tumor response to novel treatments.

Biopsies performed for this study at collaborating centers will undergo molecular analysis at MGH.

CONFIDENTIAL

This document is confidential. Do not disclose or use except as authorized.

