## 12.4 Patient Disposition

CONFIDENTIAL

This document is confidential. Do not disclose or use except as authorized.

A detailed description of patient disposition will be provided. It will include:

- A definition of patient enrollment
- A summary of data regarding patient discontinuation of study treatment
- A summary of data regarding patient inclusion and exclusion in efficacy and safety analyses

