## **12.7 Analysis of Response Rate**

Response rate will be assessed as per RECIST, see Section 8.3. Results will be reported with 95% confidence intervals.

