## **12.9 Analysis of Repeat Biopsy Complications and Results**

Complications arising from repeat tumor biopsies for genetic analyses will be recorded at the two post-biopsy required visits or at any other time that they become apparent and will be reported annually to the IRB as part of the continuing review application (unless they meet SAE reporting criteria, in which case they will be reported immediately). At the end of the study, the complications will be summarized and presented together with the rest of the study data in a descriptive fashion.

Other molecular findings from the tumor repeat biopsies at the time of clinical progression will be presented in a descriptive format.

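### If any assay fails, counting it as T790M-present is safe for the test but can inflate the reported T790M proportion, and section 12 plans no estimate or interval that would show this

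*Combined protocol and SAP*

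**What the plan says.** The primary objective (section 1.2, repeated in 12.1) has two parts, an estimate and a comparison: "To determine the proportion of patients that have a T790M mutation on their progression biopsy and to compare this with published data" for first-generation inhibitors. Section 12.2 tests a null rate of 50% against an alternative of 20% with a one-sided binomial test at 0.05. It quotes 86% power on this basis: "power calculations were performed assuming there would be 18 biopsies performed".

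Section 12.3 makes every patient who has a repeat biopsy evaluable and leaves out patients without one. For a failed assay it states: "If the results of this test are not interpretable due to technical failure of the assay, T790M will be assumed to be present". It describes this as the more conservative choice for the primary endpoint.

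Three other parts of section 12 might have covered the effect on the estimate:
- 12.4 promises "A summary of data regarding patient inclusion and exclusion in efficacy and safety analyses", but a patient with a failed assay stays included.
- 12.9 says "Other molecular findings from the tumor repeat biopsies at the time of clinical progression will be presented in a descriptive format", which concerns findings other than T790M.
- 12.7 says "Results will be reported with 95% confidence intervals", but only for response rate.

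On the use of the results, 12.1 says: "The data collected will be vital in determining the optimal strategy for future studies" comparing this drug with first-generation inhibitors.

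**The concern.** A rule that is conservative for a test need not be neutral for an estimate. Scoring a failure as positive makes it harder to conclude that T790M is less frequent than 50%, which is a proper safeguard. The same scoring also produces the headline proportion, and there it works in one direction only. Each failed sample that is really T790M-negative adds one to the numerator for a technical reason.

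The trial is a pilot of T790M as an endpoint, and its figures are meant to inform later comparative studies. With about 18 biopsies, one or two failures can move the proportion by several points. A reader given only the scored proportion could not tell how much of it came from the rule. A lesser gap is that 12.2 makes its power conditional on biopsies performed and does not say that 86% also needs every assay to be interpretable.

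**Working it through.** **Inputs.** From 12.2: n = 18, null rate 0.50, alternative 0.20, one-sided alpha 0.05, stated power 86%. From 12.3: failed assays stay in the denominator and count as positive. Not in the documents: the failure rate r and the chance q that a failed sample is truly positive. Both are assumptions and are varied below.

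**1. The plan's own figure.** P(Bin(18, 0.5) ≤ 5) = 0.0481 and P(Bin(18, 0.5) ≤ 6) = 0.1189, so the test rejects at 5 or fewer positives. Power is P(Bin(18, 0.2) ≤ 5) = 0.867. The stated 86% reproduces.

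**2. The test under the rule.** The scored count can never be below the true count, so the rule cannot raise the type I error. With f failures unrelated to status, the error is P(Bin(18−f, 0.5) ≤ 5−f): 0.0481, 0.0245 and 0.0106 for f = 0, 1 and 2.

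**3. The estimate under the rule.** Among 18 biopsies with f failures, the expected excess over the true proportion is f(1−q)/18.

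| Assumed q | f = 1 | f = 2 |
|---|---|---|
| 0.2 (failure unrelated to status, true rate 20%) | 0.8/18 = 4.4 points | 1.6/18 = 8.9 points |
| 0.5 | 0.5/18 = 2.8 points | 1.0/18 = 5.6 points |
| 1 | 0 | 0 |

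The first row corresponds to expected reported proportions of (17 × 0.2 + 1)/18 = 24.4% and (16 × 0.2 + 2)/18 = 28.9%.

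With a per-biopsy failure rate r unrelated to status, the expected reported proportion is 0.2 + 0.8r: 20.8% at r = 1%, 24.0% at 5% and 28.0% at 10%. The chance of at least one failure in 18, 1 − (1−r)^18, is 16.5%, 60.3% and 85.0% at those rates.

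**4. Two worked examples, each with 16 interpretable results and 2 failures** (exact 95% intervals, one-sided p against 50%).

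| Positives among interpretable | Scored under 12.3 | Interpretable only |
|---|---|---|
| 3 | 5/18 = 27.8% (9.7 to 53.5%), p = 0.048 | 3/16 = 18.8% (4.0 to 45.6%), p = 0.011 |
| 4 | 6/18 = 33.3% (13.3 to 59.0%), p = 0.119 | 4/16 = 25.0% (7.3 to 52.4%), p = 0.038 |

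In the first, the rule changes the estimate and not the decision. In the second it also changes the decision, in the cautious direction that 12.3 intends.

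**5. Power.** Under the rule, power at a true 20% is P(Bin(18−f, 0.2) ≤ 5−f): 75.8% with one failure and 59.8% with two. Dropping the failures and resetting the cut-off gives 75.8% (17 results, reject at ≤ 4) and 79.8% (16 results, reject at ≤ 4). With one failure, therefore, the rule itself costs nothing and the loss comes from the lost result.

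| Assumed r | Power, rule | Power, failures dropped | Cost of the rule |
|---|---|---|---|
| 1% | 84.7% | 85.0% | 0.3 points |
| 5% | 75.1% | 80.2% | 5.1 points |
| 10% | 60.9% | 76.2% | 15.2 points |

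**The case against.** The case for leaving the text alone has real force. The rule is written down in advance and its direction is disclosed. Failures may be rare: "The SNaPshot profile has been validated and is performed in a CLIA-certified lab" (section 2.3.1), section 7.1.2 asks for several cores and aspirates, 7.1.1 addresses bone sites whose processing spoils DNA, and 7.1.3 sends most of the sample to genotyping with T790M as its main use. These provisions make a 10% failure rate harder to assume, though they do not establish a low one. At 1% there is about an 83% chance of no failure at all, and then no bias. Sampling error also dominates: the exact interval for 5/18 is about 44 points wide, against a shift of 4.4 points for one failure. If the failures were counted in the report, any reader could derive the alternative figure. That last argument does not settle the matter, because section 12 does not require the count.

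Three stronger readings are tempting, and the documents do not support them. A reader might infer that the primary test is unsound; step 2 shows the opposite. A reader might infer that the reported proportion is bound to be too high; that requires at least one failure and at least one failed sample that is truly negative. A reader might infer that real power is nearer 61% or 75% than 86%; those figures rest on failure rates that the documents do not give, and part of the loss would occur under any handling of failures.

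**Conclusion.** The point holds as a cheap improvement of modest consequence. Followed exactly, 12.3 gives an upward-biased primary proportion whenever an assay fails and not every failed sample is truly positive. The 4.4 and 8.9 points for one and two failures in 18 rest on a true rate of 20% and on failure being unrelated to T790M status; the bias shrinks to zero as q approaches 1. Section 12 contains nothing that would reveal the effect, and it plans no interval for the primary proportion although it plans one for response rate. The 86% power is correct as calculated but holds only if all 18 biopsies give interpretable results.

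**What to change.** Keep the 12.3 rule for the primary test and its matching proportion. Add to 12.3:

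> *The primary proportion will be given with an exact 95% CI. As a sensitivity estimate, the T790M proportion among patients with a repeat biopsy and an interpretable T790M result will be reported with an exact 95% CI, together with the number of failed assays and the assumption that failure is unrelated to T790M status.*

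The sensitivity set should be worded in this way and not as interpretable progression biopsies. Section 7.1 allows a repeat biopsy in patients who stop for reasons other than progression, and 12.3 counts every patient with a repeat biopsy. A narrower set would mix a second change of denominator with the effect of the rule.

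In 12.2, state only that the 86% assumes all 18 biopsies give interpretable results, and that power is lower under the 12.3 rule if any assay fails. Power at assumed failure rates should not be written in, since the documents support no particular rate.

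The cost is two sentences in 12.3 and one in 12.2, with no new data and no change to the test. The downside is that two proportions are reported and the second rests on an assumption that cannot be tested. The two-sided 95% interval can also include 50% when the one-sided test rejects, as 5/18 shows, so the report should say that the test governs the decision.
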